## 4. PLANNED ANALYSES

The following analyses will be performed for this study:

- Primary analysis after the last subject completes the Month 5 study visit (after study unblinding). All available data will be analyzed.
- Supplemental analysis after the last subject completes the Month 12 study visit (Day 360).

### 4.1. FINAL ANALYSIS AFTER THE LAST SUBJECT COMPLETES THE MONTH 24 LONG-TERM FOLLOW-UP VISIT. DATA SAFETY MONITORING BOARD (DSMB)

A DSMB was established to monitor subject safety as well as data quality and adherence. Data reports for review by the members were generated from the electronic data capture (EDC) system by the IQVIA Biotech Data Management team. The IQVIA Biotech unblinded randomization statistician had a copy of the randomization schedule on hand at the closed sessions to provide the DSMB members with unblinded treatment assignments if needed.

Refer to the DSMB Charter for more details about the DSMB composition, responsibilities, and meeting frequency.

### 4.2. PRIMARY ANALYSIS

The primary analysis had taken place for this study after the last subject completes the Month 5 study visit (SAP v1.0 was finalized on 28MAR2022 and amended via memo-to-file on 22APR2022). Data used of the primary analysis was extracted and locked 29APR2022 04:04, except the potency assay. Unblinding was performed on 17MAY2022, after the transfer of potency assay data from Avotres had been completed. All analyses described in SAP v1.0 and the binding amendment plan were produced and delivered to the sponsor on 10JUN2022. This analysis formed the primary basis for the assessment of the study objectives.

All planned analyses identified in the SAP had been performed by IQVIA Biotech Biostatistics following Sponsor Authorization of this SAP, Sponsor authorization of the analysis sets, database lock (DBL), and general study unblinding.

Author:	[name]	Version Number:	2.0
Template No.:	CS_TP_BS016 Revision 6	Version Date:	23Nov2022
Effective Date:	02Dec2019	Reference:	CS_WI_BS005

### 4.3. SUPPLEMENTAL ANALYSIS

A supplemental analysis will take place for this study after the last subject completes the Month 12 study visit (Day 360). The study database will undergo an interim lock at this time. All analyses described in the current document will be produced for the supplemental analysis. This analysis will add information to the assessment of the study objectives, since data at Day 360 is generally accepted by the T1D medical community as sufficient long-term data to evaluate the efficacy and safety of a clinical candidate (AVT001). Moreover, data at Day 360 will facilitate the discussion of the development milestones for AVT001.

All planned analyses identified in the SAP will be performed by IQVIA Biotech Biostatistics following Sponsor authorization of this SAP, and database lock (DBL). The study unblinding has already occurred at the time of the primary analysis.

### 4.4. FINAL ANALYSIS

The final analysis will take place once the last subject completes the Month 24 long-term follow-up visit. The SAP amendment for the final analysis will be updated before the corresponding DBL.

## 5. ANALYSIS POPULATIONS

### 5.1. ALL SCREENED SUBJECTS ANALYSIS POPULATION

The all screened subjects (SCRN) analysis population will contain all subjects who provide informed consent for this study.

### 5.2. SAFETY POPULATION

The safety (SAF) population is defined as all subjects who receive at least one dose of study medication. If there is any doubt whether a subject was treated or not, he/she will be assumed treated for the purposes of analysis.

For analyses and displays based on SAF, subjects will be classified according to the actual treatment received.

Author:	[name]	Version Number:	2.0
Template No.:	CS_TP_BS016 Revision 6	Version Date:	23Nov2022
Effective Date:	02Dec2019	Reference:	CS_WI_BS005

## 5.3. PHARMACODYNAMIC POPULATION

The pharmacodynamic (PD) population is defined as all subjects in the safety population with at least one post-baseline assessment for the evaluation of the CD8+ T-cell reg system biomarker. If there is any doubt whether a subject was treated or not, he/she will be assumed treated for the purposes of analysis.

For analyses and displays based on PD, subjects will be classified according to the actual treatment received.

## 5.4. PROCESS FOR ANALYSIS POPULATION ASSIGNMENT

For the PD population, the identification and agreement of protocol deviations or events which affect PD results will be performed between the biostatistician, and the sponsor, prior to DBL, with sponsor authorization of any excluded subjects or their data.

# 6. GENERAL CONSIDERATIONS

## 6.1. REFERENCE START DATE AND STUDY DAY

Study Day will be calculated from the reference start date and will be used to show start/stop day of assessments and events. Reference start date is defined as the day of the first injection of study drug i.e., Day 1.

Study Day will be computed as follows:

- Study Day = (Date of event – Date of first injection of study drug) + 1 if the date of the event is on or after the date of the first injection of study drug
- Study Day = (Date of event – Date of first injection of study drug) if the date of the event is prior to the date of the first injection of study drug

In the situation where the event date is partial or missing, Study Day and any corresponding durations will appear partial or missing in the listings.

## 6.2. BASELINE

Unless otherwise specified, baseline is defined as the last non-missing measurement taken prior to the first injection of study drug (including unscheduled assessments). In the case where the last non-missing measurement and the date

Author:	[name]	Version Number:	2.0
		Version Date:	23Nov2022
Template No.:	CS_TP_BS016 Revision 6	Reference:	CS_WI_BS005
Effective Date:	02Dec2019		

and time of the first injection of study drug coincide, that measurement will be considered pre-baseline, but adverse events (AEs) and medications commencing on the date and time of the first injection of study drug will be considered post-baseline.

## **6.3. UNSCHEDULED VISITS, RETESTS, AND EARLY TERMINATION DATA**

For by-visit summaries, data recorded at the nominal visit will be presented. That is, unscheduled, retest (same visit number assigned), and early termination measurements will not be included in by-visit summaries but might contribute to the baseline timepoint and/or maximum value, where required (e.g. shift table).

Listings will include scheduled, unscheduled, retest and early discontinuation data.

## **6.4. WINDOWING CONVENTIONS**

No visit windowing for analysis purposes will be performed for this study.

## **6.5. COMMON CALCULATIONS**

Change from baseline will be calculated as:

- Change from baseline = Test value at baseline or post-baseline visit – Baseline value

Percent change from baseline will be calculated as:

- Percent change from baseline (%) = (Change from baseline at baseline or post-baseline visit / Baseline value) \* 100%

For select parameters where data is available, change and percent change will also be calculated from diagnosis.

## **7. STATISTICAL CONSIDERATIONS**

For continuous data, descriptive statistics (i.e., n [number of subjects with available data], mean, standard deviation [SD], median, 25th and 75th percentiles, and minimum, and maximum values) will be presented by treatment group and visit, when applicable.

Author:	[name]	Version Number:	2.0
Template No.:	CS_TP_BS016 Revision 6	Version Date:	23Nov2022
Effective Date:	02Dec2019	Reference:	CS_WI_BS005

For categorical data, the number and percentages of subjects in each category will be presented by treatment group and visit, when applicable

## 7.1. SAMPLE SIZE CALCULATION

The sample size of 14 subjects treated with AVT001 will provide at least 80% power to observe at least one occurrence of treatment-emergent adverse events with a true underlying incidence of 12%. The sample size provides the same power to detect at least one occurrence of local tolerability events relating to the i.v. administration of study drug.

To account for an estimated 10% potential dropout prior to the completion of the Month 5 safety/efficacy assessment post-first dose, a total sample size of approximately 24 subjects will be randomized, in a 2:1 ratio of AVT001:Placebo.

## 7.2. MISSING DATA

Missing efficacy data will not be imputed, except for missing potency assay on Visit 3/Day 1, as described in [APPENDIX 1](#).

Missing safety data will not be imputed, except for missing AE severity and relationship data (refer to [Section 17.1.1](#)). Partial or completely missing AE and medication dates will be handled as described in [APPENDIX 1](#).

## 7.3. STATISTICAL TESTS

All statistical tests will be conducted at the two-sided 5% significant level, unless otherwise specified in the description of the analyses. Confidence Intervals (CIs) will be two-sided with 95% coverage.

## 7.4. MULTIPLE COMPARISONS/ MULTIPLICITY

No adjustment for multiple comparisons and multiplicity will be performed. Only nominal *p-values* will be provided for the efficacy endpoints.

No statistical testing will be performed for the safety endpoints.

Author:	[name]	Version Number:	2.0
Template No.:	CS_TP_BS016 Revision 6	Version Date:	23Nov2022
Effective Date:	02Dec2019	Reference:	CS_WI_BS005

## 7.5. MULTICENTER STUDIES

This study will be conducted by one investigator at one center. Pooling of data for analysis is not applicable.

## 7.6. ADJUSTMENTS FOR COVARIATES AND FACTORS TO BE INCLUDED IN ANALYSES

Mixed-effect Model for Repeated Measurements (MMRM) analyses C-peptide total AUC will be adjusted for treatment group, visit, HbA1c, BMI, total daily insulin divided by weight, potency assay, and treatment group-by-visit interaction as fixed effects. See section 16.2 for further details.

## 7.7. EXAMINATION OF SUBGROUPS

No subgroup analyses are planned.

## 7.8. SOFTWARE VERSION

All analyses will be conducted using SAS version 9.4.

## 8. OUTPUT PRESENTATIONS

The presentation of data in outputs will follow IQVIA Biotech Data Display Standards. Refer to the TFL shells document for additional information.

## 9. DISPOSITION AND WITHDRAWALS

All subjects who provide informed consent will be accounted for in this study.

### 9.1. DISPOSITION

Number of subjects screened will be presented overall for the SCRN analysis population. Number and percentage of subjects with screen failure and reason for screen failure will also be presented overall based on the SCRN analysis population. Number of subjects randomized will be presented overall and by treatment group for the SCRN

Author:	[name]	Version Number:	2.0
Template No.:	CS_TP_BS016 Revision 6	Version Date:	23Nov2022
Effective Date:	02Dec2019	Reference:	CS_WI_BS005

analysis population.

Number and percentages of subjects treated, who completed/discontinued early from treatment (including reason for withdrawal), and who completed/discontinued early from the study (including reason for withdrawal) will be provided overall and by treatment group based on the SAF analysis population.

A listing showing inclusion and exclusion of each subject from each analysis population, including reason for exclusion, will be provided.

## 9.2. PROTOCOL DEVIATIONS

A listing of protocol deviations identified by the study team (important or not) will be provided.

## 10. DEMOGRAPHIC AND OTHER BASELINE CHARACTERISTICS

The following demographic and other baseline characteristics collected during the screening visit will be reported for this study:

- Age (years) – calculated relative to date of consent
- Age groups
- Sex
- Childbearing potential (for female subjects only)
- Race
- Ethnicity
- Weight (kg)
- Height (cm)
- Body Mass Index (BMI) (kg/m^2)

Continuous demographic and other baseline characteristics will be summarized using descriptive statistics overall and by treatment group based on the SAF analysis population. For categorical demographic and other baseline characteristics, number and percentage of subjects in each category will be provided overall and by treatment group based on the SAF analysis population. No statistical testing will be carried out for demographic or other baseline

Author:	[name]	Version Number:	2.0
		Version Date:	23Nov2022
Template No.:	CS_TP_BS016 Revision 6	Reference:	CS_WI_BS005
Effective Date:	02Dec2019		

characteristics.

## 10.1. DERIVATIONS

BMI, in kg/m^2, will be calculated as follows:

- BMI (kg/ m^2) = weight (kg)/ [height (m)]

## 11. SURGICAL AND MEDICAL HISTORY

Surgical and medical history are defined as any surgeries that happened before the first injection of study drug and any medical conditions/diseases that started and stopped before the first injection of study drug.

Surgical and medical history will be coded using the Medical Dictionary for Regulatory Activities (MedDRA), version 22.0, and will be summarized by System Organ Class (SOC) and Preferred Term (PT) overall and by treatment group based on the SAF analysis population. A subject having more than one surgery/medical condition/disease within the same SOC/PT will be counted only once for that SOC or PT.

All surgical and medical history will be listed.

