### 6.2 Exclusion Criteria

Subjects who meet *any* of the following criteria are *not* eligible for enrollment as study participants:

1. Poorly controlled diabetes despite insulin therapy, who in the opinion of the investigator would not be a good candidate for participation in a clinical trial
2. Screening hemoglobin <10.0 g/dL; leukocytes <3,000/uL; neutrophils <1,500/uL; lymphocytes <800/uL; platelets <100,000/uL
3. Screening Urine Albumin Excretion > 300mg/gmCr
4. Screening eGFR < 60 mL/min/1.73m^2
5. Screening ALT or AST > 1.5x upper limit of normal (ULN)
6. Screening bilirubin > 2.0 mg / dL, or > 3.0 mg / dL for participants with Gilbert's Syndrome
7. Current use of immunosuppressive or immunomodulatory therapies, including pharmacologic doses of systemic steroids (topical steroid creams and inhaled steroids without large systemic absorption are allowed).
8. Coincident medical condition likely to require immunosuppressive or immunomodulatory therapies.
9. Coincident medical condition likely to limit short term (5 year) life expectancy (malignancy, symptomatic coronary artery disease, recent stroke)
10. Prior radiation therapy, immunotherapy (within 1 year of screening), or chemotherapy
11. Serologic evidence of current HIV-1 or HIV-2 infection
12. Serologic evidence of hepatitis C infection
13. Serologic evidence of acute or chronic active hepatitis B as measured by Core Ab positive and / or Surface Antibody antigen positive
14. Subjects with other autoimmune conditions (except compensated or treated autoimmune thyroid, celiac, alopecia, or vitiligo diseases)

15. Women who are pregnant (pregnancy testing during screening), breastfeeding, or planning pregnancy during the study period.
16. Inadequate venous access to support leukapheresis.
17. Any condition that in the opinion of the investigator would preclude the subject from participating in a clinical trial.
18. Abnormal screening ECG that in the opinion of the investigator or sponsor would pose a safety risk.

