#### 11.1.2 Adverse Event

Adverse event means any untoward medical occurrence associated with the use of a drug in humans, whether or not considered drug related. Adverse events may include safety findings considered to be clinically significant by the Investigator. An adverse drug event can therefore be any unfavorable and unintended sign (including an abnormal laboratory finding), symptom, or disease temporally associated with the use of a medicinal product, whether or not it is related to the medicinal product. Reporting an adverse event does not necessarily reflect a conclusion by the Investigator that the event is causally related to the drug.

AE is any symptom, sign, illness or experience that develops or worsens in severity during the course of the study. Intercurrent illnesses or injuries should be regarded as adverse events. Abnormal results of diagnostic procedures are considered to be adverse events if the abnormality:

- results in study withdrawal
- is associated with a serious adverse event
- is associated with clinical signs or symptoms
- leads to additional treatment or to further diagnostic tests
- is considered by the investigator to be of clinical significance

A preexisting condition is one that is present at the start of the study. A preexisting condition should be recorded as an adverse event if the frequency, intensity, or the character of the condition worsens during the study period.

Each adverse event in this study will be assessed for Grade, where Grade of an AE refers to the severity of the AE. Grade will be assessed according to CTCAE Version 4.03 or higher. The CTCAE displays Grades 1 through 5 with unique clinical descriptions of severity for each AE that are based on this general guideline, with higher grades indicating worse severity.

The relationship of any AE to study treatment will be assessed using the following definitions:

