#### **11.1.4 General Physical Examination Findings**

At screening, any clinically significant abnormality should be recorded as a preexisting condition. At the end of the study, any new clinically significant findings/abnormalities that meet the definition of an adverse event must also be recorded and documented as an adverse event.

Physical examinations can be symptom-driven except at Screening, Month 5, and Month 12, during which full examinations are required.

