## 12. DISEASE HISTORY

The following disease history characteristics will be summarized overall and by treatment group based on the SAF analysis population:

- Time since diagnosis (days) – calculated relative to date of first infusion of study drug
- Use of insulin pump (yes/no)
- HbA1c at diagnosis, screening, and baseline (%)
- Change and percent change in HbA1c from diagnosis to baseline (%)
- Weight at diagnosis, screening, and baseline (kg)
- Change and percent change in weight from diagnosis to baseline (kg)
- BMI at diagnosis, screening, and baseline (kg/m^2)

Author:	[name]	Version Number:	2.0
Template No.:	CS_TP_BS016 Revision 6	Version Date:	23Nov2022
Effective Date:	02Dec2019	Reference:	CS_WI_BS005

- Change and percent change in BMI from diagnosis to baseline (kg/m^2)

All disease history characteristics will be listed.

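### SAP section 11 counts only resolved conditions as medical history, so comorbidities that began before consent and are still ongoing at first dose appear in no condition table or listing

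*Combined protocol and SAP*

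**What the plan says.** SAP v2.0 section 11 has a two-part definition. For operations it takes "any surgeries that happened before the first injection of study drug", with no further condition. For illnesses it takes "any medical conditions/diseases that started and stopped before the first injection of study drug". The history so defined is summarised by system organ class and preferred term, overall and by arm, in the safety population. The section closes with "All surgical and medical history will be listed". SAP v1.0 section 11 has the same definition, and the list of changes at the end of v2.0 does not mention it.

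Protocol Amendment 3 treats ongoing conditions as part of the safety record:

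- Section 6.2, exclusion 14, bars other autoimmune conditions, "except compensated or treated autoimmune thyroid, celiac, alopecia, or vitiligo diseases".
- Section 11.1.2 states: "A preexisting condition is one that is present at the start of the study". It adds: "A preexisting condition should be recorded as an adverse event if the frequency, intensity, or the character of the condition worsens during the study period".
- Section 11.1.4 states: "At screening, any clinically significant abnormality should be recorded as a preexisting condition".

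SAP section 12 opens with "The following disease history characteristics will be summarized overall and by treatment group based on the SAF analysis population". Its items are time since diagnosis, insulin pump use, HbA1c, weight and BMI, so it covers diabetes and no other illness.

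**The concern.** A medical-history table is where a reader looks to see whether the arms began with similar illness. Requiring that a condition has stopped keeps the resolved ones and removes the active ones. The autoimmune diseases allowed by exclusion 14 are described there as controlled, not as resolved, so they are the kind of condition that the rule would remove.

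Safety and tolerability are the primary objective. The SAP plans no statistical comparison of safety data (sections 7.4 and 17), so interpretation rests on descriptive tables. The product is intended to alter immune regulation, which makes existing autoimmune disease relevant background for its adverse events. If active comorbidity is not shown by arm, a reader cannot judge from the condition data whether the arms differed in it at the start.

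**Working it through.** The plan gives no figure on this point to reproduce. The check is to follow one case through every planned output. Take a subject with a permitted autoimmune disease that began before consent, is stable, and is still present at the first injection.

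1. **SAP section 11, medical history.** Onset before the first injection: met. Stopped before the first injection: not met. The case is in neither the summary nor the listing, because both use the same defined term.
2. **SAP section 10, demographics and baseline.** It holds age, sex, childbearing potential, race, ethnicity and body size. Comorbidity was never planned here.
3. **SAP section 12, disease history.** Diabetes only.
4. **SAP section 13, medications.** A drug ongoing at first dose is kept as concomitant and is summarised by arm and listed. The drug appears but the condition does not. A condition managed without a drug leaves no trace here. Medications therefore have a category for ongoing items, and conditions have none.
5. **SAP section 17.1, adverse events.** A prior adverse event must start or worsen between consent and first dose. A stable condition with earlier onset does not qualify. If it worsens before first dose, it is listed as a prior event. If it worsens after treatment starts, the note in Appendix 1 makes it a separate event with a new start date. The worsening is reported, but the starting state is not.
6. **SAP section 18, data not presented.** Only screening serology is named, so the omission is not a declared choice.

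Other timings show where the gap ends:

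| Condition | Where it is reported |
|---|---|
| Started and resolved before consent | Section 11 summary and listing |
| Started after consent, resolved before first dose | Section 11, and also the listing of prior adverse events |
| Started after consent, ongoing at first dose | Listing of prior adverse events |
| Type 1 diabetes | Section 12 |
| Other condition, started before consent, ongoing at first dose, not worsening | No condition output |

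The gap is therefore the last row.

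On scale, the protocol plans 16 subjects on AVT001 and 8 on placebo. One subject is 1/16 = 6.25 percentage points of the first arm and 1/8 = 12.5 points of the second. That is the coarseness of any baseline count in this trial and does not measure this defect. The documents give no prevalence for the permitted comorbidities, so the number of subjects affected is unknown and could be zero.

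**The case against.** The strongest reply is that little depends on this. Safety data are not tested, no subgroup analysis is planned (SAP section 7.7), and no repeated-measures model includes comorbidity. Protocol section 9.4 promises only key baseline characteristics, so the SAP breaks no protocol commitment. Drug-treated comorbidity leaves a by-arm trace among concomitant medications, and any worsening is still recorded as an adverse event. The table shells and CRF pages are not in the documents, so the programmed table may already include ongoing conditions.

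All of this stands as a limit on size, but it does not close the gap. A drug is indirect evidence of a condition, and a worsening shows only the subjects who worsened. Because safety is read descriptively, completeness of the descriptive tables matters. If the programs already include ongoing conditions, the SAP text is still wrong and should be made to match.

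A reader might infer more: that every ongoing illness disappears from the report, or that the section 10 baseline table is defective. The documents do not support either. Conditions that arise between consent and first dose are listed as prior adverse events, and section 10 was never meant to hold comorbidities.

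**Conclusion.** The point holds within limits and is worth correcting. Read literally, SAP section 11 leaves conditions that began before consent and are ongoing at first dose out of its by-arm summary and listing, and no other condition output reports them. The consequence is an incomplete picture of active comorbidity by arm in a trial whose primary objective is safety. No endpoint, estimate, test or sample size changes.

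The conclusion assumes that the outputs are programmed as the SAP is written. It does not depend on any assumed prevalence. A reader might also infer that the arms are in fact imbalanced or that the safety results are biased. Nothing in the documents shows either. The point is only that the planned condition outputs would not let a reader check.

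**What to change.** SAP v2.0 section 4.4 says that the SAP will be updated before the lock for the final Month 24 analysis. In that amendment:

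- Define medical history as conditions that started before consent, whether or not they have resolved, together with surgery before the first injection as now. Setting the onset limit at consent, within the period before first dose, avoids duplicating prior adverse events.
- Flag each condition as resolved or ongoing at first dose.
- Summarise both groups by system organ class and preferred term, by arm and overall, and list both.

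The cost is a short change to the definition, one rerun table and one listing. History is taken at screening and updated on dosing days (protocol sections 8.2.1 and 8.3.1), so no new visit should be needed. This assumes that the CRF records a stop date or ongoing status, which the documents do not confirm.

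There is a small downside. The Month 5 outputs were delivered on 10 June 2022, after unblinding on 17 May 2022. The revised table will differ from the delivered one, so the amendment and the table need a note saying that the definition changed and why.
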